10.10. Appendix 10: Eczema Area and Severity Index (EASI)

EASI Score Calculation: Assessment is performed on the indicated body regions, with each component (erythema, induration/papulation, excoriation, lichenification) graded on a scale of 0 to 3 and summed. The component score is then multiplied by the area score corresponding to the degree of body area involvement, followed by the weighting factor for the particular body region. (diagram from francefoundation.com and table excerpted from [Hanifin 2001](#)). Below is a sample Score.

cation. The average degree of severity of each sign in each of the four body regions was assigned a score of 0 to 3 (none, mild, moderate, and severe, respectively) with half-steps allowed. It should be

Table 1. Eczema area and severity index: calculation for patients 8 years of age and older¹

Body region	EASI Score ^{2,3}
Head/Neck (H)	$(E+I+Ex+L) \times Area \times 0.1$
Upper limbs (UL)	$(E+I+Ex+L) \times Area \times 0.2$
Trunk (T)	$(E+I+Ex+L) \times Area \times 0.3$
Lower limbs (LL)	$(E+I+Ex+L) \times Area \times 0.4$
EASI =	Sum of the above 4 body region scores

¹For children aged 0–7 years, proportionate areas were head/neck, 20%; upper limbs, 20%; trunk, 30%; and lower limbs, 30%.

²E=—Erythema, I=—induration/papulation, Ex=—excoriation, L=—lichenification.

³Where area is defined on a 7-point ordinal scale: 0=—no eruption; 1=<10%; 2=<10%–29%; 3=<30%–49%; 4=<50%–69%; 5=<70%–89%; and 6=>90%–100%.

10.11. Appendix 11: Validated Investigator Global Assessment for Atopic Dermatitis (vIGA-AD)

Below is a sample scale.

Validated Investigator Global Assessment scale for Atopic Dermatitis
vIGA-AD™

Instructions:

The IGA score is selected using the descriptors below that best describe the overall appearance of the lesions at a given time point. It is not necessary that all characteristics under Morphological Description be present.

Score	Morphological Description
0 – Clear	No inflammatory signs of atopic dermatitis (no erythema, no induration/papulation, no lichenification, no oozing/crusting). Post-inflammatory hyperpigmentation and/or hypopigmentation may be present.
1 – Almost clear	Barely perceptible erythema, barely perceptible induration/papulation, and/or minimal lichenification. No oozing or crusting.
2 – Mild	Slight but definite erythema (pink), slight but definite induration/papulation, and/or slight but definite lichenification. No oozing or crusting.
3 – Moderate	Clearly perceptible erythema (dull red), clearly perceptible induration/papulation, and/or clearly perceptible lichenification. Oozing and crusting may be present.
4 – Severe	Marked erythema (deep or bright red), marked induration/papulation, and/or marked lichenification. Disease is widespread in extent. Oozing or crusting may be present.

Notes:

1. In indeterminate cases, please use extent to differentiate between scores.

For example:

[figure not shown]
- Patient with marked erythema (deep or bright red), marked papulation and/or marked lichenification that is limited in extent, will be considered "3 – Moderate".

2. Excoriations should not be considered when assessing disease severity.

Copyright ©2017 Eli Lilly and Company – Used with the permission of Eli Lilly and Company under a Creative Commons Attribution-NoDerivatives 4.0 International License - <https://creativecommons.org/licenses/by-nd/4.0/>

10.12. Appendix 12: Severity Scoring of Atopic Dermatitis (SCORAD)

Below is a sample form.

SCORAD EUROPEAN TASK FORCE ON ATOPIC DERMATITIS		INSTITUTION PHYSICIAN	
First Name			
Last Name	Date of Birth    DD/MM/YY Date of Visit   		
			
Copyright Pr JF Stalder-ETFAD-2014			
A: EXTENT Please indicate the area involved 		B: INTENSITY 	
C: SUBJECTIVE SYMPTOMS PRURITUS + SLEEP LOSS 		SCORAD= A/5+7B/2+C 	
ORITERIA  INTENSITY  Erythema  Edema/Papulation  Oozing/crust  Excoriation  Lichenification  *Dryness 		Intensity items (average representative area) 0=absence 1=mild 2=moderate 3=severe *Dryness is evaluated on uninvolvled area	
PRURITUS (0 to 10)  SLEEP LOSS (0 to 10)  Visual analog scale (average for the last 3 days or nights)			

10.13. Appendix 13: Hand Dermatitis Investigator Global Assessment (IGA)

4-Severe: Severe erythema (deep intense red color), scaling, vesiculation (with or without erosion), and/or edema (swelling). Prominent lichenification (thickening with accentuated normal skin markings) and/or deep fissuring (causing bleeding or severe pain).

3-Moderate: Moderate erythema (prominent redness), scaling, vesiculation, and/or edema. Palpable skin thickening and/or visible fissuring affecting multiple areas of the hand.

2-Mild: Faint but definite erythema, slight but definite flaking, scattered vesicles without erosion, and/or slight but definite swelling over limited areas of the hands. Slight but definite skin thickening and/or cracked skin affecting limited areas of the hands.

1-Almost Clear: Barely perceptible erythema, flaking, and/or swelling. Minimal vesicles. Barely perceptible skin thickening and/or minimal cracked skin over limited areas of the hands.

0-Clear: No erythema, scaling, vesiculation, edema, lichenification, or fissuring. Post-inflammatory pigment alteration (either hyper- or hypopigmentation) may be present.

10.14. Appendix 14: Patient-Reported Dermatology Life Quality Index (DLQI)

Below is a sample questionnaire.

DERMATOLOGY LIFE QUALITY INDEX			
Hospital No:	Date:	DLQI	
Name:		Score:	
Address:			
Diagnosis:			

The aim of this questionnaire is to measure how much your skin problem has affected your life OVER THE LAST WEEK. Please tick  one box for each question.
			
1. Over the last week, how itchy, sore, painful or stinging has your skin been?	Very much 	A lot 	A little 
	Not at all 		
2. Over the last week, how embarrassed or self conscious have you been because of your skin?	Very much 	A lot 	A little 
	Not at all 		
3. Over the last week, how much has your skin interfered with you going shopping or looking after your home or garden?	Very much 	A lot 	A little 
	Not at all 		Not relevant 
4. Over the last week, how much has your skin influenced the clothes you wear?	Very much 	A lot 	A little 
	Not at all 		Not relevant 
5. Over the last week, how much has your skin affected any social or leisure activities?	Very much 	A lot 	A little 
	Not at all 		Not relevant 
6. Over the last week, how much has your skin made it difficult for you to do any sport?	Very much 	A lot 	A little 
	Not at all 		Not relevant 
7. Over the last week, has your skin prevented you from working or studying?	Yes 		Not relevant 
	No 		
If "No", over the last week how much has your skin been a problem at work or studying?	A lot 	A little 	Not at all 
8. Over the last week, how much has your skin created problems with your partner or any of your close friends or relatives?	Very much 	A lot 	A little 
	Not at all 		Not relevant 
9. Over the last week, how much has your skin caused any sexual difficulties?	Very much 	A lot 	A little 
	Not at all 		Not relevant 
10. Over the last week, how much of a problem has the treatment for your skin been, for example by making your home messy, or by taking up time?	Very much 	A lot 	A little 
	Not at all 		Not relevant 

Please check you have answered **EVERY** question. Thank you.

©AY Finlay, GK Khan, April 1992 www.dermatology.org.uk, this must not be copied without the permission of the authors.

10.15. Appendix 15: Patient Global Impression of Severity (PGIS)**Patient's Global Impression of Severity (PGIS) of Eczema**

Overall, how would you rate the severity of your eczema currently? (Please select one response)

- 1. None
- 2. Mild
- 3. Moderate
- 4. Severe
- 5. Very Severe

10.16. Appendix 16: Patient-Reported Outcomes Measurement Information System (PROMIS)-29

Below is a sample questionnaire.

PROMIS-29 Profile v2.1

Please respond to each question or statement by marking one box per row.

Physical Function		Without any difficulty	With a little difficulty	With some difficulty	With much difficulty	Unable to do
		5	4	3	2	1
PF11	Are you able to do chores such as vacuuming or yard work?.....					
PF21	Are you able to go up and down stairs at a normal pace?.....					
PF31	Are you able to go for a walk of at least 15 minutes?.....					
PF41	Are you able to run errands and shop?					
Anxiety		Never	Rarely	Sometimes	Often	Always
EDANX01	I felt fearful.....					
EDANX40	I found it hard to focus on anything other than my anxiety					
EDANX41	My worries overwhelmed me.....					
EDANX53	I felt uneasy					
Depression		Never	Rarely	Sometimes	Often	Always
EDDEP04	I felt worthless					
EDDEP06	I felt helpless.....					
EDDEP29	I felt depressed.....					
EDDEP41	I felt hopeless.....					
Fatigue		Not at all	A little bit	Somewhat	Quite a bit	Very much
HT	I feel fatigued					
AND	I have trouble starting things because I am tired.....					

PROMIS-29 Profile v2.1

Fatigue						
In the past 7 days...		Not at all	A little bit	Somewhat	Quite a bit	Very much
FATIGE41	How run-down did you feel on average?	 1	 2	 3	 4	 5
FATIGE40	How fatigued were you on average?	 1	 2	 3	 4	 5
Sleep Disturbance		Very poor	Poor	Fair	Good	Very good
SLEEP109	My sleep quality was.....	 5	 4	 3	 2	 1
In the past 7 days...		Not at all	A little bit	Somewhat	Quite a bit	Very much
SLEEP116	My sleep was refreshing.....	 5	 4	 3	 2	 1
SLEEP20	I had a problem with my sleep	 1	 2	 3	 4	 5
SLEEP44	I had difficulty falling asleep	 1	 2	 3	 4	 5
Ability to Participate in Social Roles and Activities		Never	Rarely	Sometimes	Usually	Always
SRPPE11_CAPS	I have trouble doing all of my regular leisure activities with others	 5	 4	 3	 2	 1
SRPPE18_CAPS	I have trouble doing all of the family activities that I want to do	 5	 4	 3	 2	 1
SRPPE23_CAPS	I have trouble doing all of my usual work (include work at home)	 5	 4	 3	 2	 1
SRPPE45_CAPS	I have trouble doing all of the activities with friends that I want to do	 5	 4	 3	 2	 1
Pain Interference		Not at all	A little bit	Somewhat	Quite a bit	Very much
PAIN11	How much did pain interfere with your day to day activities?	 1	 2	 3	 4	 5
PAIN122	How much did pain interfere with work around the home?	 1	 2	 3	 4	 5
PAIN101	How much did pain interfere with your ability to participate in social activities?	 1	 2	 3	 4	 5
PAIN104	How much did pain interfere with your household chores?	 1	 2	 3	 4	 5

PROMIS-29 Profile v2.1

Pain Intensity
In the past 7 days...

How would you rate your pain on average?

										
0 No pain	1	2	3	4	5	6	7	8	9	10 Worst pain imaginable

[figure not shown]
10.17. Appendix 17: Eczema Skin Pain and Itch Numeric Rating Scale (NRS)

Below is a sample scale.

[figure not shown]
Eczema Skin Pain and Itch Numeric Rating Scale

Individuals with eczema may experience skin pain and itch. Please indicate how severe your skin pain and itch were in the past 24 hours. Please select only one number for each item on the 0 to 10 scale (0 none and 10 worst possible).

1. Please rate the severity of your eczema-related **skin pain** at its worst in the past 24 hours.

2. Please rate the severity of your eczema-related **itch** at its worst in the past 24 hours.

[figure not shown]

10.18. Appendix 18: Atopic Dermatitis Itch Scale (ADIS)

Eczema Itching Severity Diary

[Morning Administration]

[figure not shown]
1. How would you rate your eczema-related itching **right now**?

2. Did you have **any** eczema-related itching last night? (since you last completed the diary)

Y Yes
Y No *[End of morning administration]*

3. At its **worst**, how would you rate your eczema-related itching last night?

[figure not shown]

4. To what extent did eczema-related itching impact your sleep last night?

Y No impact: itching did not affect sleep
Y Mild impact: a little difficulty falling or staying asleep due to itching
Y Moderate impact: a moderate amount of difficulty falling or staying asleep due to itching
Y Severe impact: a great deal of difficulty falling or staying asleep due to itching

Eczema Itching Severity Diary
[Evening Administration]

[figure not shown]
1. How would you rate your eczema-related itching **right now**?

2. Did you have **any** eczema-related itching today? (since you last completed the diary)

Y Yes
 Y No *[End of evening administration]*

3. At its **worst**, how would you rate your eczema-related itching today?

4. How much of the time did you experience eczema-related itching today?

Y A little of the time (less than 20% of the day)
 Y Some of the time (20% to 40% of the day)
 Y About half of the time (40% to 60% of the day)
 Y Most of the time (60% to 80% of the day)
 Y All or nearly all of the time (more than 80% of the day)

10.19. Appendix 19: Remote Endpoint Assessment Using Total Body Photography

A previous study ([Hughes 2019](#)) has described the capture of digital images of participants by site personnel, with subsequent analysis of the on-site investigator who also performed the in-person assessment. In addition, total body photography (TBP) has long been employed in dermatology for the process of “mole mapping,” ie, monitoring the development or change of nevi on the skin over time ([Rice 2010](#), [Truong 2016](#)). As such a standardized photographic series has been established to capture the entirety of the skin surface for visual evaluation ([Shriner 1990](#)).

In the assessment of AD, the well-established and validated scoring systems of the EASI (Section [10.10](#), Appendix 10: Eczema Area and Severity Index) and SCORAD (Section [10.12](#), Appendix 12: Severity Scoring of Atopic Dermatitis) are particularly well-suited for the use of photographic evaluation. Both scoring systems use regional component assessments (eg, arms, legs, chest, extremities) that correspond well to the photographic series proposed. Furthermore, the percentage of BSA involvement, itself a criterion for defining moderate-to-severe disease in AD, can be calculated separately (eg, rule of 9's approximation) or extracted from the SCORAD system.

In this study, standard AD severity assessments captured and analyzed via digital photographs will be compared with in-person investigator assessments. In addition, comparisons at 3 time points and across the treatment groups in this study will allow assessment of the utility of digital photography in the measurement of treatment effects.

For the optional digital photographic assessments, a subgroup of participants across dose groups from selected sites will provide a series of digital total body photographs at the baseline (Week 0), Week 8, and Week 16 visits.

Participants will agree to have multiple series of total body photographs taken at specified visits. Instructions and photographic guides will be provided to the sites. Captured images will be transferred and stored in a secure manner. The site investigator (at some point after the Week 20 visit), will access the images for the participants at their site and will assess the participants' severity according to the specified analyses. A central reader(s) will be selected to evaluate and score the images for all participants within the substudy.

For analysis of results, a comparison will be performed of the correlation of efficacy measures between the in-person site visit, site investigator assessment by images (including those captured by the site), and central reader assessment by images.

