8.1. Efficacy Assessments

Efficacy assessments (EASI, validated Investigator Global Assessment for Atopic Dermatitis [vIGA ADTM], percent BSA involvement, SCORAD, and Hand Dermatitis IGA) and ePRO measures (DLQI, POEM, Patient Global Impression of Severity [PGIS], Patient Reported Outcomes Measurement Information System [PROMIS]-29, Eczema Skin Pain and Itch numeric rating scale [NRS], and Atopic Dermatitis Itch Scale [ADIS]) will be performed at visits according to the Schedules of Activities. Evaluation of EASI, SCORAD, and vIGA endpoints from digital photographs will be completed from a subgroup of participants who consent to these optional substudies at selected sites.

Investigator assessments and PROs of efficacy are included in this section.

- The PRO instrument will be provided in the local language in accordance with local guidelines.
- The PRO instrument must be available for regulators and for IRB/Ethics Review Committee submissions.
- The PRO and AE data will not be reconciled with one another.

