8.1.3. Severity Scoring of Atopic Dermatitis (SCORAD)

The SCORAD is a validated tool used in clinical research and clinical practice that was developed to standardize the evaluation of the extent and severity of AD. There are 3 components to the assessment: A extent or affected BSA, B severity, and C subjective symptoms. The extent of AD is assessed as a percentage of each defined body area, and reported as the sum of all areas, with a maximum score of 100% (assigned as “A” in the overall SCORAD calculation). The severity of 6 specific symptoms of AD (redness, swelling, oozing/crusting, excoriation, skin thickening/lichenification, dryness) is assessed using the following scale: none (0), mild (1), moderate (2), or severe (3) (for a maximum of 18 total points, assigned as “B” in the overall SCORAD calculation). Subjective assessment of itch and sleeplessness is recorded for each symptom by the participant or relative on a visual analog scale, where 0 is no itch (or sleeplessness) and 10 is the worst imaginable itch (or sleeplessness), with a maximum possible score of 20. This parameter is assigned as “C” in the overall SCORAD calculation. The SCORAD is calculated as: $A/5 + 7B/2 + C$ where the maximum is 103.

Body surface area affected by AD will be assessed for each section of the body (the possible highest score for each region is: head and neck [9%], anterior trunk [18%], back [18%], upper

limbs [18%], lower limbs [36%], and genitals [1%]) and will be reported as a percentage of all major body sections combined. Body surface area will be extracted using SCORAD.

See Section [10.12](#), Appendix 12: SCORAD for a representative example of the assessment.

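### The photography substudy names correlation as its only statistic, so a systematic error in photo scores could go undetected; the handling of SCORAD component C and the deadline for image scoring are also unstated

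*Protocol*

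**What the plan says.** Protocol Appendix 19 (Section 10.19) describes an optional substudy at selected sites. Total body photographs from Weeks 0, 8 and 16 are scored by the site investigator and by one or more central readers. Photo-based severity scores "will be compared with in-person investigator assessments", and comparisons over three time points and across treatment groups "will allow assessment of the utility of digital photography in the measurement of treatment effects". For the analysis itself one statistic is named: "a comparison will be performed of the correlation of efficacy measures between the in-person site visit" and the two image-based scores.

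On what is scored, Protocol Section 8.1 states: "Evaluation of EASI, SCORAD, and vIGA endpoints from digital photographs will be completed from a subgroup of participants". Appendix 19 says that EASI and SCORAD "are particularly well-suited for the use of photographic evaluation". Section 8.1.3 defines SCORAD as A/5 + 7B/2 + C and says of component C: "Subjective assessment of itch and sleeplessness is recorded for each symptom by the participant or relative on a visual analog scale".

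On timing, Appendix 19 states: "The site investigator (at some point after the Week 20 visit), will access the images for the participants at their site". Section 6.3 keeps site personnel blinded until the last participant has finished Week 20 and the final database is locked.

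The SAP contains no photography analysis. Protocol Section 8.1.11 refers to a photography manual for scoring instructions and to a separate report for results; neither is among the documents.

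**The concern.** The substudy asks whether a photo score can stand in for an in-person score. That is a question of agreement. Correlation asks only whether the two scores lie on a straight line. If remote raters consistently score lower or higher, for instance because thickness is hard to judge in an image, the correlation can be near perfect while EASI-75 status changes.

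For SCORAD there is a second gap. Itch and sleep loss cannot be seen in a photograph, so the photo version must either omit C or borrow it, and the plan does not say which. Third, photo scores are also meant to inform treatment-effect measurement, and the protocol sets no point by which site raters must have finished while still blinded.

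What is at stake is the soundness of the separate substudy report and any later use of remote scoring that relies on it.

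**Working it through.** **1. Constant shift in EASI.** For any b > 0, corr(X, a + bX) = 1, so neither a constant nor a proportional error lowers the correlation. Take an assumed shift of -3 points at both visits:
- In person: (24 - 6.5)/24 = 17.5/24 = 72.9%, an EASI-75 non-responder.
- By photo: (21 - 3.5)/21 = 17.5/21 = 83.3%, a responder.

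The shift cancels in the numerator but not in the denominator, so percentage improvement changes.

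**2. Size over a population (illustrative).** The documents give no score distributions. The simulation assumed baseline EASI = 16 + gamma(shape 2, scale 6), capped at 72, and fractional improvement beta(2, 1.2). Correlation (r) and the concordance coefficient (CCC) were computed over baseline and one follow-up visit together.

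| Assumed photo error | r | CCC | EASI-75 in person | EASI-75 by photo |
|---|---|---|---|---|
| -3, floored at 0 | 0.999 | 0.970 | 36.0% | 48.6% |
| +3 | 1.000 | 0.969 | 36.0% | 22.7% |
| +5 | 1.000 | 0.918 | 36.0% | 14.0% |
| x 0.7 | 1.000 | 0.811 | 36.0% | 36.0% |

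With added random error of SD 2, r is 0.985 to 0.986 for the three shifts and 0.973 for the proportional error. A purely proportional error leaves EASI-75 unchanged but biases the score itself (mean -5.77 points here).

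**3. SCORAD.** The stated maximum reproduces: 100/5 + 7 x 18/2 + 20 = 20 + 63 + 20 = 103. Components A and B alone give 20 + 63 = 83, so C is 20/103 = 19.4% of the scale.
- *C omitted from the photo score.* Assume A uniform on 10 to 80, B uniform on 4 to 18, C with mean 11 and SD 5 (clipped to 0 to 20), and C correlated 0, 0.5 or 0.8 with B. Full SCORAD against A/5 + 7B/2 then gives r = 0.951, 0.971 and 0.986, with a bias of -11.0 points each time.
- *C copied from the visit.* Let the in-person and photo objective parts each have variance V and correlation ρ, let C have variance W, and let C have covariance c with each part. The correlation of the totals is (ρV + 2c + W)/(V + 2c + W). This exceeds ρ whenever ρ < 1 and 2c + W > 0. The shared term raises the correlation without any better reading of the images.

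**4. Timing.** Appendix 19 fixes the earliest time for site scoring (after Week 20) but no latest time. Section 6.3 ends the blind for site personnel once the last Week 20 evaluation is complete and the database is locked. Read together, scoring before lock is blinded and scoring after lock is not excluded.

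**The case against.** The strongest reply is that the plan promises less than a critic might assume. A reader might infer that a wrong remote score would be declared valid. The documents do not support that: they set no correlation threshold, acceptance criterion or rule for adopting remote scoring, and Appendix 19 also promises a general comparison with in-person scores. That comparison has no named method, however, so it does not close the gap.

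A reader might infer that visits will be pooled and that falling severity will inflate the correlation. Pooling is not stated, and the mention of three time points can equally mean analysis by visit.

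A reader might infer that component C will be scored from images. The text says only SCORAD, its suitability argument rests on regional components and body surface area, and the manual may deal with C. What stands is that the protocol does not say.

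A reader might infer that site raters will be unblinded. Section 6.3 protects them until lock; only the missing deadline remains.

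The EASI example is one participant chosen near the cut-off, and a -3 shift cannot occur for scores below 3. The floored simulation allows for that limit and still shows the problem.

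Finally, the trial ended early with listings only, and photographic scoring is not among its listed objectives or endpoints. That limits the consequence but does not repair the analysis.

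**Conclusion.** The point holds in a limited form. The one named analysis cannot reveal a systematic difference between photo and in-person scores. That follows from the definition of correlation and needs no distributional assumption. How far EASI-75 status would move does depend on assumptions: under those used here, shifts of 3 to 5 points move a 36.0% response rate to between 14.0% and 48.6% with r about 1.00. Whether photo scores carry any such bias is unknown.

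For SCORAD, 19.4% of the scale has no stated source, and either way of handling it makes the correlation harder to interpret. For timing, scoring after unblinding is possible under the text but is not planned.

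Severity is low. The substudy is optional, confined to consenting participants at selected sites and reported separately, and it affects no eligibility decision, dose decision or main-trial endpoint.

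**What to change.** Amend Appendix 19 as follows:
- Keep correlation if wanted, but add by visit the mean difference with 95% limits of agreement and the ICC (absolute-agreement form) for EASI, and weighted kappa for vIGA-AD. Add agreement on EASI-75 status, with baseline and follow-up taken from the same mode of assessment. The mean difference and the EASI-75 agreement matter most: in the table a single agreement coefficient stayed near 0.97 despite a 3-point shift.
- Compare objective SCORAD, A/5 + 7B/2, with a maximum of 83.
- Require image scoring to be completed before database lock and unblinding.

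The images and readers are unchanged. The cost is some extra analysis and an earlier deadline: images from the last participants would have to be scored between their Week 20 visit and lock.
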